## 4.5.2 Nutritional Supplements Exposure

Subject exposure to Vitamin D and calcium supplements will be tabulated separately in terms of total amount of IU (for Vitamin D) and mg received (for calcium), respectively, (equal to total dispensed minus total returned) and duration of exposure (date of last dose – date of first dose + 1) by treatment group using the Safety population.

Summary statistics for the average Vitamin D and calcium supplements exposure per day (= ([total dispensed minus total returned] / Duration of exposure) will also be presented separately by treatment group. Similarly, summary statistics will be provided for the average calcium supplements exposure per day.

#### 4.5.3 Adverse Events

All adverse events (AEs) will be coded by System Organ Class (SOC) and Preferred Term (PT) using the MedDRA (Version 24.0) coding system. Analyses of AEs will be performed for those events that are considered to be Treatment-Emergent Adverse Events (TEAEs). A TEAE is defined as any AE that was absent (i.e., had not occurred) or had resolved prior to the start of

study drug, and which occurred on or after the date of the first dose of study drug and within 30 days of the last dose of study drug; or any AE that started prior to the first dose of study drug, was ongoing after study treatment started, and increased in severity after the start of study drug and within 30 days of the last dose of study drug. AEs with missing onset dates will be handled according to the Conventions for Imputing Missing Dates in Appendix D.

In any tabulation of adverse events, a subject contributes only once to the count for a given SOC or PT. For summaries by severity, a subject with multiple occurrences of an AE will be represented under the most severe occurrence. For summaries by relationship to study drug, a subject with multiple occurrences of an AE will be represented under the most related occurrence.

An overall summary of the adverse events will be provided, in which the number of subjects with any adverse events, number of subjects with any TEAEs, number of subjects with any treatment-related TEAEs, number of subjects with any severe TEAEs, number of subjects with any treatment-related severe TEAEs, number of subjects with any serious TEAEs, number of subjects with any TEAES leading to study drug withdrawal, number of subjects with any TEAEs leading to study drug interruption, number of subjects with any TEAEs leading to study discontinuation, and number of subjects with any TEAEs leading to death will be summarized by treatment groups.

The following summaries will also be presented:

- TEAEs by SOC and PT
- TEAEs by SOC, PT, and region (North America and Europe)
- TEAEs by PT. Note: TEAEs will be sorted in descending order of total number of subjects with the preferred term in the abaloparatide-SC treatment group
- TEAEs by SOC, PT, and maximum severity
- Severe TEAEs by SOC and PT
- Treatment-related severe TEAEs by SOC and PT
- TEAEs by SOC, PT, and relationship to study drug
- Treatment-related TEAEs by SOC and PT
- TEAEs leading to study drug interruption by SOC and PT
- TEAEs leading to study drug withdrawal by SOC and PT
- TEAEs leading to study discontinuation by SOC and PT
- TEAEs leading to death by SOC and PT
- Serious TEAEs by SOC and PT
- Treatment-related serious TEAEs by SOC and PT
- Most common (>=5% in any treatment group) TEAEs by SOC and PT
- Non-TEAEs by SOC and PT

SOCs will be sorted in alphabetical order. Within an SOC, AEs will be sorted in descending order of the total number of subjects with the preferred term in the abaloparatide group.

To explore the relationship between TEAEs and the duration of study drug exposure, the incidence of TEAEs by time of onset ( $\leq 1$  month,  $1 < to \leq 3$  months,  $3 < to \leq 6$  months,  $6 < to \leq 9$  months, and >9 months) will be summarized by treatment group, SOC and PT. Subjects with multiple occurrences of an AE within a time period will be counted once in each time period that an onset of the AE occurs.

To evaluate the relationship between TEAEs and the antibody status, the incidence of TEAEs will be summarized by antibody status (ADA-, ADA+/Nab+, ADA+/Nab-, All ADA+, and Overall), SOC, and PT using the Antibody Population. A summary of TEAEs by PT and antibody status will also be presented, in which TEAEs will be sorted in descending order of total number of subjects with the preferred term in the overall abaloparatide-SC treatment group.

During the COVID-19 pandemic, AEs may be assessed through phone/video by the investigator conducting the study visit with subjects remotely. To explore the effect of the COVID-19 pandemic on reported AEs, summaries of TEAEs by SOC and PT, TEAEs leading to treatment discontinuation, and serious TEAEs will also be presented:

- by subject's study status relative to COVID-19 pandemic onset (subjects who completed or withdrew from the study before 01 March 2020, vs subjects who completed or withdrew from the study on or after 01 March 2020)
- by AE onset dates relative to COVID-19 pandemic onset (AE occurs before 01 March 2020, vs AE occurs on or after 01 March 2020)
- by region (North America and Europe)

The number of subjects with any TEAEs, the number of subjects with any SAEs, and the number of subjects with TEAEs leading to study drug withdrawal will also be summarized by treatment group, SOC, PT and age group (< 65, 65 - < 75, and  $\ge$  75 years). Similar tables will be provided by treatment group, SOC, PT and BMI group (BMI < 25, 25  $\le$  BMI < 30, and BMI  $\ge$  30).

Subject listings will be provided for all AEs by SOC and PT. Listings will also be produced for deaths, SAEs, AEs leading to study drug withdrawal and study discontinuation, and severe AEs. A listing for subjects who are anti-PTH or anti-PTHrP positive and had adverse events will also be presented.

A data listing for COVID-19 related AEs (AE PTs related to COVID-19 using MedDRA Version 24.0) will be prepared by SOC and PT. A listing of subjects who experience an Unanticipated Adverse Device Effect (UADE) will be provided from the Pharmacovigilance database.

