6.2. Study Schedule

This study is comprised of 9 clinic visits. Study assessments are to be performed according to the Schedule of Assessments and Procedures (Table 3). There is $a \pm 4$ -day window for each clinic visit.

The study will consist of a Screening Period (up to 2 months), a Pretreatment Period (1 week), a Treatment Period (12 months), and a Follow-up Visit (1 month). During the Treatment Period, subjects will have clinic visits for study-related protocol procedures at Day 1, Month 1, Month 3, Month 6, Month 9, and Month 12. The active phase of the study will be considered complete when the last subject undergoes the last visit. For the purpose of this study, 1 month is equal to 30 days.

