## 1.2 Study Design

## 1.2.1 Synopsis of Study Design

This is a randomized, double-blind, placebo-controlled, Phase 3, multicenter study enrolling approximately 225 subjects at up to 40 study centers designed to evaluate the efficacy and safety of abaloparatide-SC 80  $\mu$ g per day for the treatment of osteoporosis in men at high risk for fracture. The study will consist of a Screening Period (up to 2 months), a Pretreatment Period (1 week), a Treatment Period (12 months), and a final study visit one month after the last dose of study medication (Follow-up visit). Eligible subjects will be randomized, on a 2:1 basis, to receive either abaloparatide-SC 80  $\mu$ g per day or placebo injections for 12 months to determine the effect of abaloparatide on lumbar spine BMD and other bone health-related endpoints. All subjects will receive calcium 500-1000 mg/day and vitamin D 400-800 IU/day, or a dose determined by the Investigator and agreed by the Sponsor Medical Monitor, according to the subject's need. Both treatment groups of subjects will undergo protocol-specified procedures (Schedule of Events, Table 1), including BMD and fracture assessment. The study design is presented in Figure 1.

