#### **3** GENERAL STATISTICAL METHODS

### 3.1 Sample Size Planned and Specified in the Protocol

A study sample size of 225 subjects (150 in the abaloparatide-SC group and 75 in the placebo group) will provide at least 99% power to detect a mean difference of 6.5% in the percentage change from baseline in lumbar spine BMD at 12 months between the abaloparatide-SC and the placebo groups at a two-sided alpha level of 0.01, assuming a standard deviation (SD) of 6.0% and a drop-out rate of 10%. For the key secondary endpoints, a total sample size of 225 subjects will have 96% power to detect a 2.2% mean difference (SD=3.5%) of percent change in total hip BMD at 12 months, and 80% power to detect a 2.0% mean difference (SD=4.1%) of percent change in femoral neck BMD at 12 months.

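### The TEAE onset table compares periods of 1, 2, 3, 3 and about 4 months without person-time, so its percentages cannot be read across time within an arm

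*SAP*

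**What the plan says.** SAP section 4.5.3 gives the table its purpose: "To explore the relationship between TEAEs and the duration of study drug exposure, the incidence of TEAEs by time of onset". The five onset periods are up to 1 month, over 1 to 3, over 3 to 6, over 6 to 9, "and >9 months) will be summarized by treatment group, SOC and PT". A subject with repeated occurrences "will be counted once in each time period that an onset of the AE occurs".

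The last period has no stated upper end, but the TEAE definition in the same section closes it: an event qualifies if it is one "which occurred on or after the date of the first dose of study drug and within 30 days of the last dose". SAP section 1.2.1 describes "a Treatment Period (12 months), and a final study visit one month after the last dose of study medication", and Protocol section 6.2 fixes the unit: "1 month is equal to 30 days".

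No denominator is given for this table. Neither document mentions person-time, exposure-adjusted rates, a number at risk per period, or a time-to-event analysis of adverse events. SAP section 4.5 makes safety analyses descriptive, without formal testing unless otherwise specified.

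**The concern.** A table meant to show how adverse events relate to length of exposure is naturally read across its columns: is the event more frequent early or late? Here the columns cover unequal lengths of time, and the last is about four times as long as the first. A man has more chance of an onset in a longer period even if his underlying rate never changes. The within-arm pattern therefore mixes period length with any real change in rate, and nothing planned for the table separates the two.

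What is at stake is the description of early versus late tolerability of a daily injection over 12 months. A stable event could be described as accumulating with exposure, and an event that settles could be described as persistent. No efficacy claim and no test depends on the table.

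**Working it through.** The documents state no figure for this table, so there is none to reproduce. The monthly event rates below are assumptions. The period limits, the 30-day tail and the 10% drop-out come from the documents.

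**Inputs.** Cut points at 1, 3, 6 and 9 months (SAP 4.5.3). Treatment for 12 months (SAP 1.2.1). TEAE window closing "within 30 days of the last dose of study drug" (SAP 4.5.3). Month of 30 days (Protocol 6.2). Planning value: "a drop-out rate of 10" percent (SAP 3.1).

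**Step 1: period lengths.** The cuts fall at days 30, 90, 180 and 270, and the window ends at day 360 + 30 = 390. The lengths are 30, 60, 90, 90 and 390 − 270 = 120 days, that is 1, 2, 3, 3 and 4 months. About 3 of the last 4 months are on drug.

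**Step 2: constant rate.** With rate λ per month and t months at risk, the share of men with at least one onset in a period is 1 − exp(−λt). The first five result columns assume full follow-up. The final column applies 10% drop-out with all treated men as denominator.

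| λ per month | ≤1 | 1–3 | 3–6 | 6–9 | >9 | Last/first | Last/first, 10% drop-out |
|---|---|---|---|---|---|---|---|
| 1% | 1.00% | 1.98% | 2.96% | 2.96% | 3.92% | 3.94 | 3.61 |
| 2% | 1.98% | 3.92% | 5.82% | 5.82% | 7.69% | 3.88 | 3.56 |
| 5% | 4.88% | 9.52% | 13.93% | 13.93% | 18.13% | 3.72 | 3.40 |
| 20% | 18.13% | 32.97% | 45.12% | 45.12% | 55.07% | 3.04 | 2.79 |
| 50% | 39.35% | 63.21% | 77.69% | 77.69% | 86.47% | 2.20 | 2.02 |

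At 0.1% per month the two ratios are 3.99 and 3.66.

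**Step 3: the drop-out column.** Assume exponential drop-out with 10% lost by Month 12: μ = −ln(0.9)/12 = 0.00878 per month. Each man stays at risk for 1 month after his last dose, so mean time at risk in the last period is (0.9^(8/12) − 0.9)/μ = (0.9322 − 0.9000)/0.00878 ≈ 3.66 months per treated man, against 1.00 in the first. That is the rare-event ratio of 3.66. Using men at risk at the start of each period as denominator gives 3.87 at λ = 1%, so an at-risk percentage alone does not remove the artefact. Counting only the 3 on-drug months of the last period (full follow-up) gives 2.97.

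**Step 4: a falling rate.** Rates of 4%, 2%, 1.33%, 1.33% and 1% per month make λt = 0.04 in every period, so each shows 1 − exp(−0.04) = 3.92%. This pattern is constructed to show what is possible, not what is likely. A less contrived case is a month-1 rate four times a 1% baseline. It gives 3.92, 1.98, 2.96, 2.96 and 3.92%, with the first and last periods equal.

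**Step 5: against placebo.** With placebo at the 1% baseline (1.00, 1.98, 2.96, 2.96, 3.92%), the ratios of abaloparatide-SC to placebo in that second case are 3.94, 1, 1, 1 and 1. Period length cancels. If drop-out were 20% in one arm and 10% in the other, equal rates would show ratios of 1.00, 0.99, 0.97, 0.94 and 0.91 for the higher-loss arm under an all-treated denominator.

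**Step 6: person-time.** Subjects with onset per 100 person-months at λ = 1% are 1.00, 0.99, 0.99, 0.99 and 0.98. In the month-1 excess case they are 3.92, 0.99, 0.99, 0.99 and 0.98. For very common terms, dividing by the whole period overcorrects: at 50% per month it gives 39.35, 31.61, 25.90, 25.90 and 21.62. Stopping each man's time at his first onset in the period removes this, because expected onsets are 1 − exp(−λt), expected time is (1 − exp(−λt))/λ, and their ratio is λ.

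**The case against.** The strongest reply is that the trial has a randomised placebo arm and the table is shown by treatment group. Both arms share the same periods, so a reader who compares arms period by period is not misled by their length. This stands. A reader might infer that an early excess over placebo would be hidden, but Step 5 shows that it would not. Only unequal drop-out disturbs that comparison, and the documents give no reason to expect it.

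Four further points also stand in part.

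- **The size.** Four-fold is a ceiling that needs rare events and complete follow-up.
- **The denominator.** A reader might infer that men who have left remain in the later percentages. The SAP does not say so. It restricts denominators in sections 4.5.6 and 4.5.7 and uses the whole Safety population for a date-split medication table in 4.5.9, so neither can be presumed here.
- **Existing information.** SAP 4.5.1 tabulates exposure duration at the same cut points by arm, and 4.1 plans a Kaplan-Meier plot of withdrawal. A reader could approximate the number still on drug at each cut.
- **Other displays.** Adverse events of special interest get onset-time summaries with fine early bins, and local tolerance, hypercalcemia and orthostatic hypotension are summarised by visit. A reader might infer that early versus late tolerability rests on this table alone, which is not so.

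None of this repairs the within-arm reading. The special-interest onset table also has unequal bins and no person-time, and numbers at risk alone leave most of the artefact. The comparison with placebo does not show how an arm's own rate changes with exposure, which is the table's stated question.

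**Conclusion.** The point holds for reading across periods within an arm. As specified, period length alone produces a last-to-first ratio of up to about 4 under a constant rate. At 10% drop-out with all treated men as denominator, it is about 3.4 to 3.7 for uncommon terms (0.1% to 5% per month) and about 2 to 3 for very common ones (20% to 50% per month). A declining rate could look flat. Comparison with placebo within a period is largely sound unless drop-out differs.

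These sizes rest on assumed constant rates, exponential drop-out and the once-per-period counting rule. The period lengths are the plan's own. Because the analysis is exploratory and descriptive, this is a worthwhile improvement to one table. It does not threaten the trial's conclusions.

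**What to change.** In SAP section 4.5.3:

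- Keep the planned counts.
- For each period and arm, add the number of men at risk at the start of the period and the number with an onset per 100 person-months at risk. State the denominator of any percentage shown. End a man's time at his first onset of that term within the period, so that common terms are not overcorrected.
- Show the 30 days after each man's last dose as a separate period, so that the onset periods describe time on drug only.
- Say that any statement about duration of exposure will rest on these rates and on the comparison with placebo.

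The cost is SAP wording and a little programming from dose and onset dates already held. The table also grows: five on-drug periods and one post-dose period in two arms make 12 rates per row. Limiting the rates to SOCs and common PTs would contain this.

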## **Adverse Events of Special Interest**

An adverse event of special interest (AESI) is an AE that is designated to be of special medical or scientific interest to the Sponsor. There are four major categories of AESIs as follows:

- Injection site reaction AEs -- Skin reaction AEs at the injection site
- Skin AESIs -- AEs of eschar, ulcer, or non-healing wounds at the injection site
- Hypersensitivity AESIs -- TEAEs in the Hypersensitivity Standardized MedDRA Query (SMQ narrow)
- Other AESIs:
  - Orthostatic hypotension

Study BA058-05-019 SAP

- Tachycardia
- Nausea
- Hypercalcemia
- Hypercalciuria
- Hypophosphataemia

The MedDRA PTs, High Level Terms (HLT), and SMQs used to identify the AESIs are stored in the study folder in the Biometrics SAS Environment.

An overall summary of the treatment emergent AESIs will be provided, in which the number of subjects with any adverse events, number of subjects with any TEAEs, number of subjects with any treatment-related TEAEs, number of subjects with any severe TEAEs, number of subjects with any treatment-related severe TEAEs, number of subjects with any serious TEAEs, number of subjects with any treatment-related serious TEAEs, number of subjects with any TEAES leading to study drug withdrawal, number of subjects with any TEAEs leading to study drug interruption, number of subjects with any TEAEs leading to study discontinuation, and number of subjects with any TEAEs leading to death will be summarized by treatment group.

The treatment emergent AESIs will be summarized by PT and SOC for each of the AESIs. Summary of the onset time and duration of the treatment emergent AESIs will be provided by treatment group using descriptive statistics (number of subjects, mean, SD, median, interquartile range, minimum and maximum). The number of subjects in each of the onset time groups (1 day, 2-3 days, 4-7 days, 8-15 days, 16-29 days, 1 to <2 months, 2 to <6 months, 6 to <10 months, and >=10 months) and duration groups (1 day, 2-3 days, 4-7 days, 8-15 days, 16-29 days, and >= 30 days) will also be summarized by treatment group.

To evaluate the relationship between AESIs and the antibody status, the incidence of treatment emergent AESIs will also be summarized by antibody status (ADA-, ADA+/Nab+, ADA+/Nab-, All ADA+, and Overall), SOC, and PT for the abaloparatide SC group.

An overall summary of the treatment emergent AESIs, as described above, will also be presented by treatment group (and overall) and the following subgroups:

- Age group (< 65, 65 < 75, and  $\ge$  75 years).
- BMI group (BMI <  $25, 25 \le$  BMI < 30, and BMI  $\ge 30$ )
- Region (North America and Europe).

Subject listings will be provided for each of the AESIs.

## 4.5.4 Anti-Abaloparatide Antibody

For subjects in the abaloparatide-SC group, the anti-abaloparatide antibody assessment in the serum samples for immunogenicity testing will be categorized by two outcomes:

- Negative for anti-abaloparatide antibodies
- Positive for anti-abaloparatide antibodies

The number (%) of subjects in the above categories of abaloparatide antibodies will be summarized at Day 1 (Visit 3), Month 1 (Visit 4), Month 3 (Visit 5), Month 6 (Visit 6), Month 9 (Visit 7), Month 12 (Visit 8) and the Follow-up Visit scheduled approximately 1 month after the last dose of study medication (Month 13/Visit 9) using the Antibody population.

For those subjects with anti-abaloparatide antibody present (i.e, are ADA positive), the titer level, the presence of neutralizing anti-abaloparatide antibodies (negative or positive), and the assessment outcomes for cross-reactivity to PTH (negative or positive) and PTHrP antibodies (negative or positive) together with the neutralizing antibody status in subjects that are positive for PTH (negative or positive for the presence of PTH-neutralizing antibodies) or PTHrP (negative or positive for the presence of PTH-neutralizing antibodies) will be summarized by study visit. Figures for the incidence of antibody and neutralizing antibody for the anti-abaloparatide, anti-PTH, and anti-PTHrP will be presented by nominal visit.

All antibody information collected for the abaloparatide-SC group will be presented in a data listing.

The results of antibody analyses will be presented in a separate report.

## 4.5.5 Local Tolerance

Local tolerance will be assessed by the investigator and by the subject separately.

## **Investigator Assessment of Local Tolerance**

For each local skin reaction symptom, descriptive statistics (number of subjects, mean, SD, median, interquartile range, minimum and maximum) will be used to summarize the responses on the 4-point scale (0=None, 1=Mild, 2=Moderate,3=Severe) by treatment, visit and timepoint. In addition, for each symptom, the number (%) of subjects in each response category (none, mild, moderate, and severe) will be provided by treatment per visit and timepoint.

Investigator assessment of local tolerance was not scheduled for Month 12 in the protocol. Investigator assessments recorded on Month 12/Early Termination (Month 12/ET) CRFs will be summarized under the "End of Treatment" visit.

The maximum severity of each symptom of local skin reaction per subject will be summarized with the number (%) of subjects in each response category (none, mild, moderate, and severe) by treatment and visit. The maximum severity of each symptom of local skin reaction per subject will also be summarized with the number (%) of subjects in each response category by treatment and timepoint (and at post-dose timepoint).

The maximum severity of symptom scores will also be summarized descriptively (number of subjects, mean, SD, median, interquartile range, minimum and maximum) for each response on the 4-point scale (0=None, 1=Mild, 2=Moderate, 3=Severe) by treatment and visit, and by treatment and timepoint, respectively.

During the COVID-19 pandemic, the investigator's assessment of the symptoms of local skin reactions may be assessed through alternative methods other than direct on-site assessment. To explore the effect of the COVID-19 pandemic, summaries of the investigator's assessment of local tolerance will also be presented by:

- region (North America and Europe)
- subject's study status relative to COVID-19 pandemic onset (subjects who completed or withdrew from the study before 01 March 2020, vs subjects who completed or withdrew from the study on or after 01 March 2020)

• excluding local tolerance assessments made via alternative methods other than direct on-site assessment

